12.4. Statistical Analyses

Include analysis of primary efficacy endpoints, secondary endpoints, safety analyses, and any planned interim analyses

Data analysis will be performed with SAS (Cary, NC) version 9.4 and R (Vienna, Austria) version and 3.6+. After verifying the normality of distribution of the continuous variables, the mean and standard deviations will be calculated. If data are not normally distributed, log transformation will be conducted. All analyses will also be conducted after controlling for age, gender, and BMI.

Specific Aim 1: Using pre-test data, random forest will be applied to identify associations between 48 amino metabolites, BP phenotypes (including SBP or DBP), and 24-hour urinary excretion to predict the classification of study subjects and will be achieved by R program. For urinary metabolites nominated by the random forest analysis, generalized linear model (GLM) will further be performed to generate p values and false discovery rates (FDR) to correct for testing multiple urinary metabolites using the Benjamini-Hochberg procedure.

Specific Aim 2a: Using both pre and post-test data, feasibility will be assessed by measuring: 1) % subjects who come to the 8-week follow-up; 2) number of education sessions attended online (intervention group); 3) % days that subject log his/her meals using mobile dietary app; and, 4) % days that subject log in-home BP using BP monitor device. The preliminary effect of SRD on the outcome variables will be tested by using a repeated measures analysis of variance (RM-ANOVA) with one between-subjects factor (intervention and control) and one within-subject factor (pre-test and post-test).

Specific Aim 2b: We estimate that 20 participants/group will provide sufficient data for estimating intervention effects on metabolomic profiling and reduction of urinary sodium level and BP. The estimated effect size will be used for sample size justification and power analysis for a future larger study.

Specific Aim 3: Using pre-test data, analysis of targeted genotyping will be conducted by the R program. A moderator analysis will be used to determine whether the relationship between urine metabolites or sodium intake and BP depends on the SS candidate gene (GNAI2 SNPs).

All testing will be two-sided and p<0.05 or FDR < 10% will be considered as significant.

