The study results will increase knowledge regarding how the SRD alters the urinary metabolome in pre-hypertensive patients, investigating associations of salt sensitivity and within- and between-person variations in the SRD intervention, and exploring how these alterations may improve BP control and cardiovascular health. Also, it will provide foundational information for future work on developing personalized nutrition interventions to reduce dietary sodium intake through identified mechanisms.

3. Objectives and Endpoints *All data points collected in the study should support an objective or have a regulatory purpose.* *Complete the table – add rows as needed.*

3.1. Objective(s) Clearly and concisely define the primary and secondary outcomes.	3.2. Endpoint Clearly define the endpoints. (endpoints are the basis for concluding that the objective has been met).	3.3. Justification for Endpoint Briefly explain why the endpoint(s) were chosen.

 To examine the associations of urine metabolites with urinary sodium levels and BP control. 	
 The metabolite profiles identified in this study will provide insight into the mechanisms underlying changes in sodium intake and BP levels in hypertension. 	
 Previous studies in our team found some novel metabolites which are reflecting dietary sodium intake using targeted urinary metabolites.

 To determine the feasibility, preliminary efficacy, and estimate of the effect size of sodium- 	
 Findings of the study will help develop effective interventions to improve sodium restricted 	
 Numerous studies have shown that low-sodium diet can reduce blood pressure and improve cardiovascular outcomes.

restricted diet intervention on changes in metabolomics profiling and BP reduction among 40 pre-hypertensive patients.	diet adherence and cardiovascular outcomes.	

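### Aim 1's FDR < 10% is not assured if Benjamini-Hochberg counts only metabolites that a random forest picked on the same baseline data and a related outcome

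*Combined protocol and SAP*

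**What the plan says.** Section 12.4 (Specific Aim 1) describes two steps, both on baseline data. In the first, "random forest will be applied to identify associations between 48 amino metabolites, BP phenotypes (including SBP or DBP), and 24-hour urinary excretion", with the stated purpose "to predict the classification of study subjects". In the second, "For urinary metabolites nominated by the random forest analysis, generalized linear model (GLM) will further be performed to generate p values" and false discovery rates "to correct for testing multiple urinary metabolites using the Benjamini-Hochberg procedure". The same section adds "All analyses will also be conducted after controlling for age, gender, and BMI" and sets the significance rule "p<0.05 or FDR < 10% will be considered as significant".

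The objective in section 3.1 is "To examine the associations of urine metabolites with urinary sodium levels and BP control". Its endpoint in section 3.2 is the list that results: "The metabolite profiles identified in this study will provide insight into the mechanisms underlying changes in sodium intake and BP levels in hypertension".

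Five things are not stated: the class that the forest predicts, the GLM outcome, the rule and number for nomination, the number of tests that BH counts, and any hold-out set, cross-fitting or other allowance for selection. Section 12.2 gives 40 participants, says that the study is underpowered, and limits quantitative results to feasibility and pilot use.

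**The concern.** BH holds its level when null p values are valid and every test that could have been reported is counted. The wording attaches the p values and the FDRs to the nominated metabolites. The variables named for the forest are those of the objective, blood pressure and urinary sodium, so the reading that fits best is that the forest and the GLM look at the same or related outcomes. A metabolite then reaches the GLM because it already tracks the outcome in these 40 people. Its p value is likely to be small even if it is null, and BH divides by k instead of 48.

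At stake is the label on the Aim 1 list. Metabolites reported at FDR < 10% could carry that rate or several times it, and a reader could not tell which. The list could then enter later work with the wrong error rate.

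**Working it through.** **Inputs.** From section 12.4: 48 metabolites, FDR level 10%, p<0.05, three covariates. From section 12.2: n = 40. Assumed, because the documents give no figure: the number nominated k, the nomination rule (top k by forest importance or by a simple rank screen), the correlation between metabolites, the relation between forest target and GLM outcome, and the number and size of true associations.

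**The plan's own figure.** The 10% is a chosen level, so there is no calculation to reproduce. As a benchmark, BH at 10% over all 48 metabolites gave 8.9% to 10.4% in simulation.

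**Bound.** Within k nominated metabolites, the BH cut-off at rank i is 0.10 × i/k = (0.10 × 48/k) × i/48 = (4.8/k) × i/48. A metabolite's rank among the nominated never exceeds its rank among all 48. So whatever BH rejects within k is also rejected by BH over 48 at level 4.8/k. With no true association and independent p values, the chance of any false discovery is therefore at most 4.8/k, whatever the nomination rule:
- k = 10: 48%
- k = 15: 32%
- k = 20: 24%
- k = 36: 13%
- k = 48: 10%

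Taking the k smallest of 48 uniform p values (200,000 draws) gave 48%, 32%, 24%, 13% and 10%, so the bound can be reached at these k.

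**Simulation, shared outcome, BH over the nominated only.** n = 40, linear model with three covariates. Forest cells: 1,000 runs each (Monte Carlo standard error up to 1.6 points), with the range over a continuous and a median-split target. Rank screen (absolute difference between the two halves of a median split): 4,000 runs.

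| Setting | Top 10 | Top 20 |
|---|---|---|
| Forest, no true association, correlation 0 | 33–44% | 22–25% |
| Forest, no true association, correlation 0.3 | 28–33% | 19% |
| Forest, six true associations, correlation 0 | 25–31% | 18.5–20% |
| Rank screen, no true association, correlation 0 | 37% | 23% |
| Rank screen, correlation 0.3 | 30% | 19% |
| Rank screen, correlation 0.6 | 19% | 12% |
| Rank screen, correlation 0.8 | 13% | 9% |

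**Forest target only partly related to the GLM outcome.** Rank screen, uncorrelated metabolites, no true association, 10,000 runs. For target-outcome correlations of 0, 0.3, 0.5, 0.7 and 1:
- top 10: 10%, 13%, 18%, 25%, 38%
- top 20: 10%, 12%, 15%, 18%, 24%

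**Where the inflation disappears.**
- Forest target independent of the GLM outcome: 7.2% to 11.0%.
- Forest kept as a filter but BH family held at 48: 5.3% to 9.8%; with the rank screen, 3% to 11% across the correlations above.

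**The significance rule.** If p<0.05 alone were enough for Aim 1, the chance of at least one false positive among 48 independent null tests would be 1 − 0.95^48 = 0.915, about 91%.

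**Several outcomes.** If BH at 10% is run separately for SBP, DBP and urinary sodium, the chance of at least one false list, with no true association and independent outcomes, is 1 − 0.9^3 = 27%.

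**The case against.** The strongest reply is that the plan is under-specified, not wrong. The phrase on correcting for multiple metabolites could mean a family of 48. Blood pressure and sodium excretion could be inputs to the forest and the class something else. The objective in section 3.1 does not define the forest's target. Few metabolites might be screened out. The first two of these readings give no inflation, and the third gives little. This stands, and it is why the point is conditional.

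A second reply is that independent metabolites give the largest figures. This also stands: at correlation 0.8 the excess nearly vanishes even with a shared outcome, and the documents give no correlation.

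A third is that this is a pilot. Section 12.2 lowers the consequence, but it does not make the FDR label correct, and section 12.4 still calls results significant on that label.

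A reader might infer that the Aim 1 error rate is certainly inflated several-fold. The documents do not support that: it needs a shared or closely related outcome, a small k, a BH family of k and weak correlation together, and none of these is stated. A reader might also infer that p<0.05 overrides BH. The rule's wording allows it, but it can equally be read as p<0.05 for single tests and FDR for the metabolite tests.

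**Conclusion.** The concern holds in conditional form. If the forest target and the GLM outcome are the same or related, and BH counts only the nominated metabolites, FDR < 10% is not assured. The effect ranges from none to several-fold. The 4.8/k bound rests only on independent p values and no true association. The simulated figures rest on assumed nomination rules, correlations and effect sizes; they illustrate the range and are not estimates for this trial.

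This is more than missing detail: followed as it most naturally reads, the plan lets the outcome choose the tests, and a better method costs almost nothing. The consequence is limited to the labelling of an exploratory baseline list. No comparison between arms is affected. The point should be fixed, with medium confidence because it depends on the reading.

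**What to change.** - Name the Aim 1 outcomes: SBP, DBP and 24-hour urinary sodium.
- For each, fit the covariate-adjusted GLM for all 48 metabolites and apply BH at 10% with 48 as the family, or pool all 3 × 48 = 144 tests in one BH family. If BH is run per outcome, say that the 10% applies to each list separately.
- Keep the forest as a descriptive ranking, or as a filter with the BH family held at the full count. State its target and nomination rule.
- State that FDR < 10% alone governs Aim 1 and any other analysis that tests many metabolites or SNPs, which includes the metabolomic part of Aim 2 and the moderator analysis of Aim 3. Reserve p<0.05 for genuinely single tests.

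The cost is a few sentences in section 12.4 and 48 regressions per outcome, with no new data. The downside is that fewer metabolites will be called significant.

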8.6. Other Research Procedures (e.g., other safety and efficacy assessments.)

Digital self-monitoring for diet and in-home monitoring of BP will be recorded automatically via wearable fitness tracker and wireless BP monitor over 8 weeks. The following data will be collected by self-reported questionnaire or relevant health equipment. Informed consent will be obtained either at pre-study visit (Day -1) or baseline visit (Day 1).

- Individual characteristics (baseline): We will collect demographic information such as age and gender.
- Physical Assessment (baseline and 8-week): Height, weight, and blood pressure will be measured at baseline and 8-week.

8.7 Attach a Schedule of Activities (SOA) Excel File [Download the Template here: [Schedule of Activities](#)]

Check to indicate that the SOA Excel File is attached →

9. Preparation/Handling/ Storage/Accountability of Investigational Drug, Biologic, or Device

N/A - This study does not include any investigational products (e.g. drugs, devices or biologics)

N/A - An Investigator Brochure is attached

N/A - A Drug/Device Manual is attached

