12.2. Sample Size Determination

Include number of participants to recruit, screen, and enroll to have adequate power to test the key hypotheses for the study. Provide all information needed to validate your calculations and judge the feasibility of enrolling and following the necessary number of participants.

Given the pilot nature of the study, we will recruit 40 participants and conduct a stratified randomized clinical trial. Specifically, 40 subjects will be recruited, and block randomized to either an intervention or a control group in a 1:1 ratio. Per power analysis, the study will be underpowered; therefore, quantitative outcomes will be interpreted only as feasibility and pilot data. A sample size of 40 subjects will give us adequate sample size to provide meaningful confidence intervals for our estimates of feasibility and preliminary effects. With this overall sample size, we expect to have sufficient diversity of input on the intervention components to plan refinements prior to testing in a larger intervention trial.

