12.3. Populations for Analyses

Clearly identify and describe the analysis datasets (e.g., which participants will be included in each).

For data analysis, we will include data from study participants who have completed baseline and follow-up survey, and anthropometric and biomarker measurements.

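### The Aim 2a RM-ANOVA names no tested term and does not adjust for the outcome's baseline value; ANCOVA would give narrower intervals unless the pre/post correlation is high

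*Combined protocol and SAP*

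**What the plan says.** Section 12.4, Specific Aim 2a: "The preliminary effect of SRD on the outcome variables will be tested"; the method is given as "tested by using a repeated measures analysis of variance (RM-ANOVA) with one between-subjects factor (intervention and control", with "one within-subject factor (pre-test and post-test" as its second factor. The pre-test value is therefore one of the two repeated outcomes, not a covariate. No term (group, time or group-by-time) is named as the test of the intervention.

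The opening paragraph of 12.4 adds: "All analyses will also be conducted after controlling for age, gender, and BMI". The outcome's own baseline value is not in that list. Nor is it said which BMI is meant, although section 8.6 provides two: "Height, weight, and blood pressure will be measured at baseline and 8-week".

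For Aim 2b the plan states: "The estimated effect size will be used for sample size justification and power analysis for a future larger study". No estimator or interval method is given for that effect size. Section 12.2 concedes that the study is underpowered and defends 40 participants as an "adequate sample size to provide meaningful confidence intervals for our estimates of feasibility and preliminary effects". Section 12.3 limits the analysis to completers: "we will include data from study participants who have completed baseline and follow-up survey".

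**The concern.** A two-group, two-time RM-ANOVA produces three tests, and they answer different questions. Group-by-time compares mean change between arms, which is what the section 12.1 hypotheses need. The group main effect averages the pre-test, where randomized arms do not differ in expectation, with the post-test, so it estimates half the effect. The time effect is not a between-arm contrast at all. An analyst could follow 12.4 to the letter and carry a halved effect into the next trial's sample size.

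Even with group-by-time named, the analysis makes poor use of the baseline. A change score subtracts the whole baseline value, whatever its correlation with the 8-week value. ANCOVA subtracts only the fraction the data support. At 20 per arm the baseline difference between arms has a standard error of √(2/20) = 0.32 SD. At a correlation of 0.5 with equal SDs, an imbalance of that size moves the change-score estimate by (1 − 0.5) × 0.32 = 0.16 SD in the opposite direction; ANCOVA corrects for it.

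The plan itself treats the estimate and its interval, not a p-value, as the quantitative product of Aim 2. Lost precision therefore bears on the stated purpose. Eight-week BMI is a further risk: it is measured after randomization and a diet programme could change it, so adjusting for it could remove part of the effect.

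**Working it through.** **Inputs from the documents.** 40 participants randomized 1:1, so 20 per arm (12.2); two-sided 5% level, 2×2 RM-ANOVA, covariates age, gender and BMI (12.4).

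**Assumed, because the documents give no value.** Pre/post correlation ρ from 0.3 to 0.95; equal pre and post SDs (set to 1) unless stated; true effect 0.5 SD; covariates unrelated to the outcome; 16 completers per arm as a dropout case.

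**The plan's own figure.** N = 40 cannot be reproduced: no effect size, SD, power or target interval width is given. For context, a comparison of 8-week values alone at 20 per arm has about 35% power at 0.5 SD, which agrees with the plan's admission of low power.

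**Step 1: the tested term.** The group-by-time F equals the squared t on change scores. On a simulated data set, t = −2.771 on 38 df and F = 7.677 = t². For the group main effect the expected estimate is (0 + 0.5)/2 = 0.25, and the SD of a subject's mean is √((1+ρ)/2) = 0.81, 0.87 and 0.92 at ρ = 0.3, 0.5 and 0.7. Power is 16%, 14% and 13%.

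**Step 2: interval width, equal SDs.** With n per arm and no other covariates:

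- change score: variance = 2(1−ρ) × 2/n, with 2n−2 df;
- ANCOVA: variance = (1−ρ²) × 2/n × (1 + 1/(2n−4)), with 2n−3 df.

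At ρ = 0.5 and n = 20 the half-widths are 2.024 × √(1 × 0.1) = 0.640 and 2.026 × √(0.75 × 0.1 × 1.028) = 0.563, a ratio of 0.88. Simulation (20,000 trials per setting) gives the results with age, gender and BMI in both models. Half-widths are in SD units, change score vs ANCOVA:

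| ρ | No covariates (formula) | Three covariates in both (simulated) | ANCOVA narrower by | Share of trials with narrower ANCOVA interval |
|---|---|---|---|---|
| 0.3 | 0.757 vs 0.620 | 0.785 vs 0.643 | 18% | 99% |
| 0.5 | 0.640 vs 0.563 | 0.665 vs 0.584 | 12% | 95% |
| 0.7 | 0.496 vs 0.464 | 0.515 vs 0.483 | 6% | 82% |
| 0.8 | 0.405 vs 0.390 | 0.421 vs 0.405 | 4% | 70% |
| 0.9 | 0.286 vs 0.283 | 0.298 vs 0.295 | 1% | 50% |
| 0.95 | 0.202 vs 0.203 | 0.210 vs 0.211 | none | 36% |

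Both estimators averaged 0.50. In the models without covariates, simulated type I error was 0.048–0.051 for group-by-time and 0.048–0.052 for ANCOVA, and the formulas cross at ρ ≈ 0.94 with 20 per arm (≈ 0.93 with 16). With 16 per arm the gains at ρ = 0.3, 0.5 and 0.7 are again 18%, 12% and 6%.

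**Step 3: unequal SDs.** Let k be the ratio of 8-week to baseline SD. The per-subject variances become 1 + k² − 2ρk (change) and k²(1−ρ²) (ANCOVA). At ρ = 0.3, 0.5 and 0.7, k = 0.8 gives gains of 28%, 23% and 19%; k = 1.25 gives 10%, 4% and about nil, and about 2% wider at ρ = 0.8.

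**Step 4: power at 0.5 SD, group-by-time to ANCOVA.** Without covariates: 26% to 36%, 34% to 42%, 51% to 57% at ρ = 0.3, 0.5 and 0.7. With the three covariates in both: 24% to 33%, 31% to 39%, 48% to 53%.

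**Step 5: sizing a future trial.** For 80% power at 0.5 SD with equal SDs, n per arm = 2(z₀.₉₇₅ + z₀.₈₀)² V/0.25, which is 62.8 V with unrounded z. Change-score sizing, V = 2(1−ρ) = 1.4, 1.0, 0.6, gives 88, 63 and 38. ANCOVA sizing, V = 1−ρ² = 0.91, 0.75, 0.51, gives 58, 48 and 33.

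**The case against.** The best case for leaving the plan alone has four parts.

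- **Group-by-time is the conventional reading.** The hypotheses are between-arm, the model has a pre/post factor, and one sentence would settle it. This is fair: the halved main effect is a possibility left open, not a likely outcome.
- **The comparator.** Section 12.4 may mean an unadjusted RM-ANOVA plus an adjusted one, and covariates entered only as main effects leave the group-by-time test unchanged at 38 df. Against a change score with no covariates, covariate-adjusted ANCOVA is only 14%, 8% and 2% narrower at ρ = 0.3, 0.5 and 0.7, and 1% wider at 0.8. Those figures are correct, but they mix two choices. They charge ANCOVA for age, gender and BMI, which the plan already wants. Like for like, the gain is 18%, 12% and 6% with or without those covariates.
- **Equal SDs flatter ANCOVA for blood pressure.** Entry requires SBP 120–159 or DBP 80–99 mmHg, which can compress the baseline spread. An assumed truncation of baseline to −1 to +1.5 SD leaves gains of 8%, 5% and 2%. This stands as a limit on size; because either criterion suffices, real truncation is partial.
- **It is a declared pilot.** Power has little weight, and planners can compute ρ from the same data and choose either sizing formula. With 40 people an observed ρ of 0.5 has a 95% interval of about 0.22 to 0.70. This weakens the power and future-n figures, but not the point about interval width, which is the plan's own justification for 40.

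Also, section 12.2 does promise intervals for preliminary effects; what is missing is how they will be obtained.

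**Conclusion.** The concern holds as a matter of precision and specification. The group-by-time test is unbiased with correct type I error under randomization, subject to the completer-only set. The group main effect keeps its type I error but does not estimate the full treatment effect, so the term must be named.

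Replacing the change-score contrast by ANCOVA narrows the interval by 6% to 18% for correlations of 0.7 down to 0.3, by 1% to 4% at 0.9 to 0.8, and not at all near 0.95. These figures assume equal SDs and the same other covariates in both models. A larger SD at 8 weeks can reduce the gain to zero or a loss of about 2%; a smaller one increases it. Neither the correlation nor any SD is in the documents, so the actual gain is unknown. The possible loss is small, and the change should be made before the data are analysed.

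**What to change.** Amend section 12.4, Aims 2a and 2b:

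- For urinary sodium, SBP, DBP and each metabolite, regress the 8-week value on arm, the baseline value of the same outcome, age, gender and baseline BMI (not 8-week BMI), plus any stratification factor actually used. Section 12.2 calls the randomization stratified but names no factor, so that must be settled first.
- Keep the plan's log-transformation and FDR rules for the metabolites.
- Report the adjusted mean difference with its 95% confidence interval, the residual SD and the observed pre/post correlation as the Aim 2a/2b result.
- If RM-ANOVA is retained, make it secondary and name group-by-time as the tested term.

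The analysis set stays as in section 12.3; ANCOVA does not cure its restriction to completers.

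Cost: SAP wording and no new data. Against a change-score model with the same covariates, ANCOVA uses one more residual degree of freedom (34 rather than 35 at 20 per arm) and carries a variance factor of 1 + 1/33 = 1.03, which cancels the gain at ρ of about 0.95.
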